**RANDOMIZED CONTROLLED PILOT STUDY USING PROPRANOLOL TO
DECREASE GENE EXPRESSION OF STRESS-MEDIATED BETA-
ADRENERGIC PATHWAYS IN HEMATOPOIETIC STEM CELL
TRANSPLANT RECIPIENTS**

Version 3.0

Principal Investigator: [name]
Medical College of Wisconsin
[name]
[name]
[contact]
[contact]
Email: [contact]

Co-Investigator: J. [name], MS
CIBMTR
Froedtert and the Medical College of Wisconsin
Clinical Cancer Center
[name]
[name]
[contact]
[contact]
Email: [contact]

Co-Investigator: [name], MS
Froedtert and the Medical College of Wisconsin
Clinical Cancer Center
[name]
[name]
[contact]
[contact]
Email: [contact]

Consultant
and Statistician: [name]
UCLA-David Geffen School of Medicine
[name]
[name]
[name]
[contact]
Email: [contact]

Sponsor: Medical College of Wisconsin

Funding Sponsor: This project has an offer of sponsorship from
the National Cancer Institute, National Institutes of Health,
under Contract No. HHSN261200800001E.

PROTOCOL SYNOPSIS

Randomized Controlled Pilot Study Using Propranolol to Decrease Gene Expression of Stress-Mediated Beta-Adrenergic Pathways in Hematopoietic Stem Cell Transplant Recipients

Principal Investigator: [name]

Study Design: This is a randomized controlled pilot study designed to evaluate whether the beta-adrenergic antagonist propranolol is effective in decreasing gene expression of stress-mediated beta-adrenergic pathways among a cohort of individuals receiving an autologous hematopoietic stem cell transplant (HCT) for multiple myeloma.

Primary Objective: The primary objective of this study is to assess whether beta-blocker administration to individuals undergoing HCT alters genome-wide transcriptional pathways involved in beta-adrenergic signaling.

Secondary Objectives: Explore the impact of socioeconomic status, depression, and anxiety on gene expression as well as on the relationship between beta-blocker and gene expression; assess clinical feasibility and efficacy.

Eligibility: Eligible patients are between 18 and 75 years undergoing autologous HCT for treatment of multiple myeloma who are \leq 1 year since initiation of systemic anti-myeloma therapy and who have had no prior progression or relapse of myeloma prior to HCT. They must have an ECOG performance status of 0 or 1, and have a stem cell graft with $>2.0 \times 10^6$ CD34+ cells/kg available for transplant. Patients are excluded if they have had a prior autologous HCT, are on a beta-blocker at the time of study entry, have a previous intolerance to beta-blockers, have any medical contraindications to beta-blockers therapy, or have active depression.

Treatment Description: Patients enrolled in this study will be randomized to either receive propranolol or not starting 7 (\pm 2) days prior to transplant and continuing through 28 days post-transplant. Propranolol will start at 20mg

twice daily and will be titrated to 40mg twice daily as tolerated.

Accrual Objective: 40 patients will be enrolled to the clinical trial.

Accrual Period: The estimated accrual period is 9 months.

Study Duration: It is estimated that the entire duration of the study will not exceed one year as follow-up is 30-45 days.

Glossary of Study Abbreviations

AE:	adverse events
ANC:	absolute neutrophil count
CC:	Cancer Center
CR:	complete response
CRC:	clinical research coordinator
CTCAE:	Common Terminology Criteria for Adverse Events
CTRA:	conserved transcriptional response to adversity
DSM:	Data and Safety Monitoring
DSMC:	Data and Safety Monitoring Committee
ECOG:	Eastern Cooperative Oncology Group
FCBP:	Female of Child Bearing Potential
G-CSF:	granulocyte-colony stimulating factor
HADS:	Hospital Anxiety and Depression Scale
HCT:	hematopoietic stem cell transplantation
HED:	human equivalent dose
ICSR:	Individual Case Safety Reports
IMWG:	International Myeloma Working Group
IRB:	Institutional Review Board
MCW:	Medical College of Wisconsin
MM:	multiple myeloma
nCR:	near complete response
OS:	overall survival
PFS:	progression-free survival
PI:	Principal Investigator
SES:	socioeconomic status
sCR:	stringent complete response
SNS:	sympathetic nervous system
TRM:	treatment-related mortality
UCLA:	University of California Los Angeles
VGPR:	very good partial response

Table of Contents

1.0 BACKGROUND AND RATIONALE	7
1.1 Beta-adrenergic signaling in the tumor microenvironment	7
1.2 Beta-blockade and cancer	7
1.3 Propranolol dosing for cancer control	8

1.1 Beta-adrenergic signaling in the tumor microenvironment

Research suggests beta-adrenergic signaling regulates multiple cellular processes that contribute to the initiation and progression of cancer, including inflammation, angiogenesis, apoptosis/anoikis, cell motility and trafficking, activation of tumor-associated viruses, DNA damage repair, cellular immune response, and epithelial–mesenchymal transition.¹ Within the tumor microenvironment, beta-adrenergic receptors on tumor and stromal cells are activated by catecholamines from local sympathetic nerve fibers (norepinephrine) and circulating blood (epinephrine). Studies of beta-adrenergic influence on tumor biology were motivated by epidemiologic observations in humans associating stressful life circumstances with accelerated progression of incident cancers.² In several experimental cancer models, activation of the sympathetic nervous system (SNS) has been shown to promote the metastasis of solid epithelial tumors and the dissemination of hematopoietic malignancies via beta-adrenoreceptor-mediated pathways.⁴ SNS regulation of cancer cell biology and the tumor microenvironment is helping to clarify the molecular basis for long-suspected relationships between stress and cancer progression, and now suggests a highly leveraged target for therapeutic intervention.¹

1.2 Beta-blockade and cancer

Retrospective epidemiologic studies have linked the use of beta-blockers to reduced rates of progression for several solid tumors.⁵⁻⁹ Recently, a retrospective case-control study of MM patients identified that concurrent use of any beta-blocker is associated with more favorable 5-year overall and disease-specific survival.¹⁰ Preclinical pharmacologic and biomarker studies in animals are now laying the groundwork for translation of beta-blockade as a novel adjuvant to existing therapeutic strategies in clinical oncology, linking the use of beta-adrenergic antagonists (beta-blockers) with reduced disease progression in humans.^{4-9, 11-17} Further, propranolol, a non-selective beta-adrenergic receptor blocker, has apoptotic and anti-proliferative effects on multiple myeloma (MM) cells.¹⁸ Propranolol is the most studied nonselective beta-blocker;¹⁹ this, along with its safe side effect profile, cost-effectiveness, and efficacy in vitro in preventing tumor progression as compared to selective beta-antagonists^{1, 16, 20} make it our preferred beta-blocker for use in the current proposal. Propranolol does not have any significant drug interactions with the more common antineoplastic (melphalan) and infection-related drugs utilized to treat MM.

The first 30 days following autologous hematopoietic stem cell transplantation (HCT) generally constitute the time period around transplantation of greatest psychological and physiological stress and inflammatory processes.^{21, 22} Psychosocial stress gradually improves over time with a return to pre-transplant psychosocial functioning by about one year post-transplant.^{23, 24} Therefore, it follows that the first 30 days may also be the time period of highest beta-adrenergic signaling due to increased stress response. Further, data

from mouse models have demonstrated that beta-blockade with propranolol 8 days prior to exogenous stress exposure is effective in blocking beta-adrenergic signaling at the tumor level.⁴ Tumor metastasis in mouse models is increased 30-fold as compared to the control group after 20 days of exposure to chronic stress.²⁵

1.4 Socioenvironmental impact on gene expression

Stress-induced beta-adrenergic signaling within the tumor microenvironment also results in alterations in SNS-mediated gene expression; this was identified in an ovarian cancer cohort of 10 individuals with elevated biobehavioral risk factors compared to relative grade- and stage-matched individuals without these risk factors.³¹ This type of socioenvironmental impact on gene expression has been consistently demonstrated, with previous studies showing that circulating immune cells show a systematic shift in basal gene expression profiles during extended periods of stress, threat, or uncertainty, consistent with the physiology of stress-associated illness.³²⁻³⁶ Recently, we identified increased expression of genes mediated by beta-adrenergic signaling in a cohort of HCT recipients with acute myelogenous leukemia in first complete remission (N=78) under conditions of increased stress as measured by low socioeconomic status (SES) (unpublished data). These changes associated with low SES are reciprocally associated with increased relapse and leukemia-free survival (unpublished data). It is unknown, however, whether a nervous system-targeted intervention such as beta-blocker therapy would affect change at the level of gene expression.

Evaluating a molecular outcome with the magnitude of data that is available as with gene expression studies allows us to assess biobehaviorally-mediated biological changes between two differing groups utilizing a small cohort, as has been done previously.^{31, 35} This design provides the advantage of conducting a small, short-term, and inexpensive

pilot study to first assess the feasibility and tolerability of administering a beta-blocker to a cohort of HCT recipients while also obtaining novel information on potential mechanisms.

1.5 Rationale

There has never been a prospective human trial prophylactically administering beta-blocker therapy with conventional cancer treatments to affect change at the level of the tumor microenvironment. We aim to implement the first human pilot study using a beta-blocker to pharmacologically intervene in biobehaviorally mediated gene expression in cancer patients to expand our previous findings. Specifically, we aim to evaluate this effect among patients receiving HCT for MM, the number one indication for autologous transplantation at MCW as well as in the US and worldwide. Using an autologous rather than allogeneic HCT population will minimize the number of potentially confounding variables for purposes of this study. The long-term goal is to utilize findings from this study to alter tumor progression.

2.0 STUDY DESIGN

This is a proof of concept randomized controlled pilot study assessing whether gene expression of beta-adrenergic signaling pathways can be altered in individuals undergoing autologous HCT for MM by administering a daily beta-blocker (propranolol) to 20 participants. Outcomes of patients on this clinical trial will be compared to 20 participants in a control arm. Study assessment time points are detailed in Table 4.7a.

2.1 Primary Objective

The primary objective of this study is to assess whether beta-blocker administration to individuals undergoing HCT alters genome-wide transcriptional pathways involved in beta-adrenergic signaling.

2.2 Secondary Objectives

The secondary objectives of this study are:

- 1) To explore additional gene expression endpoints including:
 - a) the impact of SES, depression, and anxiety on gene expression as well as on the relationship between beta-blocker administration and gene expression profiles
- 2) To assess clinical feasibility and efficacy by
 - a) testing the feasibility (adherence, tolerance) of using beta-blockers with an intensive conventional antineoplastic treatment regimen (autologous HCT) in a cancer population
 - b) describing meaningful clinical endpoints between the intervention vs. control arms including depression and anxiety, proportion of

patients developing engraftment syndrome, time to neutrophil and platelet engraftment, incidence of infection, myeloma response, treatment-related mortality, progression-free survival, and overall survival

2.3 Patient Eligibility

2.3.1 Inclusion Criteria

Patients with multiple myeloma receiving an autologous HCT are eligible when the following criteria are met:

1. 18-75 years of age
2. ≤ 1 year since initiation of systemic anti-myeloma therapy
3. Patient is scheduled for autologous hematopoietic stem cell transplant as the upfront therapy for their multiple myeloma
4. Karnofsky Performance Status of $\geq 80\%$; patients eligible for HCT are eligible for the study
5. All men and women must agree to practice effective contraception during the study period if not otherwise documented to be infertile.

2.3.2 Exclusion Criteria

1. Prior autologous HCT
2. Non secretory multiple myeloma
3. Concurrent beta-blocker therapy at or within 3 weeks of study entry. Refer to section 2.4.4 for complete list.
4. Previous intolerance to beta-blocker therapy
5. Any medical contraindications to beta-blocker therapy including, but not limited to, symptomatic hypotension; drug hypersensitivity; sinus bradycardia, sick sinus syndrome, or 2nd or 3rd degree atrioventricular block without a pacemaker; uncompensated heart failure; or uncontrolled asthma
6. Active, untreated depression screened for by the HCT physician (Patients who screen positive will be offered a referral to the MCW Psycho-Oncology program for further evaluation and treatment)
7. Concurrent use of medications in section 2.4.4 throughout the study or within one week of study entry.
8. Pregnant or lactating women

2.4 Treatment Plan

The study drug will be dispensed. Compliance will be monitored by the clinical research coordinator (CRC). Beta-blocker tolerability will be assessed clinically by the treating physician on a weekly basis and for 1 week following cessation of beta-blocker therapy; subjects will be questioned about specific side effects as well as assessed for blood pressure and heart rate during weekly appointments or by phone.

2.4.2 Study interruption

Participants needing to stop beta-blocker therapy secondary to intolerance or new onset of a contraindication will not be considered for resumption of therapy. Outcome and medical data will continue to be collected and assessed for intervention arm participants despite an inability to remain on beta-blocker therapy for the study duration.

2.4.3 Beta-blocker weaning

Beta-blocker will be weaned for one of three reasons: 1) completion of drug intervention (28 ± 2 days post-transplant), 2) intolerance secondary to side effects, or 3) onset of new medical symptoms rendering beta-blocker therapy as contraindicated (see section 2.3.2). For patients that are at 40 mg twice daily at the time of weaning, the dose will be reduced to 20 mg twice daily for one week before being discontinued entirely. For patients who are on 20 mg twice daily at the time of weaning, their dose will be stopped altogether.

2.4.4 Prohibited concomitant medications and treatments

- *Beta-Blocker therapy* including but not limited to: Atenolol, Carvedilol, Labetalol, Metoprolol, Nadolol, Propranolol, Sotalol, Timolol
- *Pgp substrates*: Bosutinib, PAZOPanib, Silodosin, Topotecan, VinCRIStine (liposomal)
- Ceritinib, Floctafenine, Methacholine
- *Herbal medications*, including but not limited to: St. John's Wort, ginko biloba, saw palmetto, and ginseng

2.4.5 Concomitant medications to be used with caution: Require an investigational drug pharmacist consult to evaluate drug interaction

- Full list can be found in Appendix A
- **Antihypertensives and bradycardia causing agents:**
 - *Alpha1 blockers*, including but not limited to: Doxazosin, Prazosin, Tamsulosin; Terazosin
 - *Alpha2 agonist*, including but not limited to: CloNIDine, GuanFACINE, TiZANidine
 - *Alpha/Beta-Agonist*: Dopamine, DOPamine; EPINEPHrine; Isomethcptene; Levonordefrin; Norepinephrine
- **Scheduled and As Needed Beta2-Agonist therapy**: Albuterol; Arformoterol; Bambuterol; Fenoterol; Formoterol; Indacaterol; Levalbuterol; Metaproterenol; Olodaterol; Pirbuterol; Salmeterol; Terbutaline; Vilanterol
- *Pgp substrate*: Afatinib, Colchicine, DOXOrubicin, Dabigatran, Edoxaban, Everolimus, Rivaroxaban, vincristine
- *Strong Cyp1A2 inducers*, including but not limited to: CarBAMazepine, PHENobarbital, Rifampin
- *Strong Cyp1A2 inhibitors*, including but not limited to: Cipro, FluvoxaMINE, Primaquine
- *Cyp1A2 Substrates*, including but not limited to: Vemurafenib
- *Strong Cyp2D6 inhibitors*, including but not limited to: BuPROPion, Cinacalcet, FLUoxetine, Lopinavir, PARoxetine, Ritonavir, Terbinafine
- *Cyp2D6 Substrates*, including but not limited to: Abiraterone

2.5 Study Drug Information

Propranolol is highly protein bound (89%) and undergoes extensive first-pass metabolism (hepatic extraction ratio 0.7-0.9) yielding nonrestrictive elimination where the hepatic extraction ratio is greater than the amount of unbound drug. This results in significant intra-patient variability. At higher doses used to achieve serum concentrations >30 ng/ml, propranolol manifests linear kinetics.^{30,37} Owing to this unique pharmacokinetic profile it is difficult to calculate a predicted serum concentration. However, given that a mouse serum concentration target of 20 ng/ml has been established and that this theoretically correlates with target human serum concentration,^{25,38} we can apply human dose-finding studies to determine HED need to achieve said concentration. At a dose of 120 mg/day mean serum trough concentrations have been reported as 54 ± 34 ng/ml and 41.6 ± 37.6

ng/ml while peak serum concentrations are >100 ng/ml.^{39, 40} The optimal cardiac dose has been established at 144 mg/day, yielding a serum trough concentration of 30 ± 7 ng/ml; however, some have suggested concentrations > 20 ng/ml manifest cardiac effects.⁴⁰ Similarly, other studies associate propranolol 80 mg/day with serum concentration in the 10 to 30 ng/ml range.^{28, 29, 41} Therefore, a goal dose of 40 mg orally twice daily in humans should achieve similar serum concentrations as that demonstrated in mice to affect cancer progression, with the possibility that the anxiolytic dose of 20 mg twice daily may have similar effects. Drug supply and storage will be coordinated with the F/MCW Clinical Trials Office.

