Drug adherence will be measured as a percentage of the prescribed number of pills that were actually taken (either 20 mg or 40 mg twice daily). This will be determined outpatient via pill count on Day -2 and Day +28 and inpatient through nursing documentation. Patients will have one additional pill count upon return of the study supply of propranolol. The return will occur at the next earliest clinic appointment following discontinuation of the propranolol. There is no consensual standard for what constitutes adequate adherence. Clinical trials report average adherence rates of 43 to 78 percent among patients taking drugs for chronic conditions; some clinical trials define rates above 80% as acceptable.⁴³ A target adherence rate of 80% will be utilized in this study to constitute having adequately retained the patient in the study. Adherence will be recorded as a continuous (0-100%) variable. Adherence will be assessed separately during two time periods – prior to transplant (between Time 1 and Time 2) and from transplant through Day +28 (Time 2 to Time 3). Patients will be included in final analyses if and only if they have been adherent (at least 80% of the prescribed dose) to the study drug during the designated time period.

As the retention rate (participants' ability or inability to be maintained on the study drug) will necessarily be affected by side effects, we will collect side effect data to better

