inform the feasibility aim of this study. Common side effects that will be screened for clinically at follow up time points include fatigue, dizziness, constipation, bradycardia, hypotension, depression, insomnia, weakness, disorientation, nausea, diarrhea, hypersensitivity reaction, purpura, alopecia, and impotence. Any side effects deemed secondary to beta-blocker usage will be documented and appropriately treated or referred for treatment collaboratively by the study PI and treating HCT physician, and beta-blocker therapy will be weaned by 20 mg at each dosing time. Patients will remain at the weaned dose for 1 week prior to discontinuing if this dose decrease does not eliminate the drug entirely. Heart rate and blood pressure will be monitored and documented at baseline, once after initiating beta-blocker therapy but before transplant, just prior to transplant, and weekly thereafter; these are two of the most common and dangerous side effects. Given that patients aren't as acutely medically ill pre-transplant and that standard of care following beta-blocker initiation would involve follow-up weeks later, this schedule should allow for adequate study drug monitoring while minimizing patient study visit burden. Blood pressure less than 90/55 or heart rate less than 50 will prompt clinical review by the study PI and treating HCT physician for appropriateness to continue beta-blocker therapy. Calendar collection of adverse events (AEs) will be obtained through toxicity forms (Common Terminology Criteria for Adverse Events [CTCAE]) completed weekly until neutrophil engraftment occurs (absolute neutrophil count $> 500/\text{mm}^3$ for ≥ 3 consecutive days) and bi-weekly thereafter until the study endpoint at Week 6 (See Tables 2a and 2b). Further details about AE monitoring are included in Section 4.3.

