4.4 Specimen Collection

The Cancer Center Lab draw blood to be stored in PAXGene RNA tubes at three study time points as described in Table 4.7b. These time points include baseline (Day -7), Day -2 (immediately prior to transplant, central line placement, or administration of any conditioning regimen), and Day +28. Blood will be drawn at one of two locations: in the hospital (if participants are immediately post-transplant and/or still or re-hospitalized) or in the transplant clinic during their regular visits. The PAXGene RNA tubes do not require any additional processing of blood samples before being frozen and sent to UCLA. These PAXGene RNA tubes will be stored at -80C in the Neuroscience Research Center, which is a locked facility, until they are batched and shipped to University of California Los Angeles (UCLA) for gene expression analysis. Before being stored they will be assigned a dummy ID that will be the sole identifier of the samples. The linked identifiers will be stored on a secure computer network through the CIBMTR under the PI's name. Samples will be packaged with dry ice and shipped overnight to [name] lab at UCLA at the time of study conclusion. This will be done on a day such that the UCLA lab can receive and keep the samples frozen at -80C. Our groups have collaborated successfully on transfer of samples in the past. All samples will be sent together.

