Primary analyses will be performed at the time of all 3 blood draws (Baseline, Day -2, and Day +28) and will use general linear model analyses to quantify the association between expression of each of the 53 CTRA contrast genes and beta-blocker usage. To ensure analysis of patients with sufficient beta-blocker exposure, only gene expression data from study participants with an adherence rate of 80% (at either dose) will be used as comparators against the control group. Descriptive tables of patient-, disease-, and transplant-related factors will be prepared with separate columns by propranolol vs. no propranolol groups. Any demographic or psychosocial variables (other than those of primary interest) that are unevenly distributed between groups after randomization will be adjusted for in subsequent analyses as previously described using ANCOVA. Further, differences in gene expression will be compared between groups/variables that might not have been randomly distributed, regardless of beta-blocker treatment assignment, to ascertain whether these differences may be stronger than drug-attributed changes. The UCLA Social Genomics core will provide genetic and statistical analyses for gene expression data.

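### The 80% adherence filter measures intake, not exposure at the draw, and Day +28 samples may be taken after weaning, so a null gene result could not be attributed to blockade having no effect

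*Combined protocol and SAP*

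**What the plan says.** **The filter.** Section 5.3.1: "To ensure analysis of patients with sufficient beta-blocker exposure, only gene expression data from study participants with an adherence rate of 80" per cent qualify, and the sentence goes on "at either dose) will be used as comparators against the control group". Patients on 20 mg and on 40 mg twice daily therefore pass alike.

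**How adherence is measured.** Section 3.2.2.1: "This will be determined outpatient via pill count on Day -2 and Day +28 and inpatient through nursing documentation". It is assessed separately before transplant and from transplant to Day +28. One further count is made when unused drug is returned.

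**What is said about exposure.** Section 2.5 says of the drug's metabolism: "This results in significant intra-patient variability". It adds: "Owing to this unique pharmacokinetic profile it is difficult to calculate a predicted serum concentration". It then uses published human data to support the goal dose and places 80 mg/day at 10 to 30 ng/ml, against a target of 20 ng/ml taken from the mouse.

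**When blood is drawn.** Section 4.4 fixes draws by study day (baseline, Day -2, Day +28), in hospital or "in the transplant clinic during their regular visits". It sets no clock time or interval since the last dose and asks for neither to be recorded. A footnote to Table 4.7a lets the 4-week research sample be taken within 7 days either side of its target. Section 2.4.3 starts weaning at Day 28 ± 2.

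**What else is recorded.** Section 3.2.2.1: "Heart rate and blood pressure will be monitored and documented at baseline", before transplant and weekly after it. Table 4.7b does not limit this row to the propranolol arm. Section 5.3 makes no use of these data.

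**The concern.** The filter is given a job that it cannot do. Taking at least 80% of prescribed tablets shows that drug was swallowed. It does not show what concentration resulted, or whether the patient was still on drug when the RNA sample was taken. The protocol itself says that the first does not follow from dose, and its two calendars allow the second to fail.

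This matters because the study is a proof of concept, with about 15 treated patients in the gene analysis, and is meant to supply effect sizes for later trials. If the CTRA profile does not differ between arms, the planned analysis holds nothing that separates two explanations: blockade does not change expression, or blockade was weak or absent at the draw. If some samples are off drug, the effect size passed to the next trial is diluted by an unknown amount.

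**Working it through.** **1. The plan's own dose figure.** Section 1.3 converts with human dose = mouse dose (mg/kg) × 3/37 × body weight. Mouse weight is not given; 0.020 kg is assumed.
- Upper: (0.5/0.020) × 3/37 × 60 = 121.6 and × 70 = 141.9 mg/day (plan: 122 and 142).
- Lower, divided by 21 days: 5.8 and 6.8 mg/day (plan: 6 and 7).
- Midpoints: 63.7 and 74.3 mg/day (plan: 60 to 80).

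The figures reproduce. The goal dose is the middle of a range whose ends differ 21-fold, so the derivation does not fix exposure.

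**2. Spread in Section 2.5** (± read as SD).

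| Daily dose | Trough, ng/ml | SD/mean | Trough per mg of daily dose |
|---|---|---|---|
| 120 mg | 54 ± 34 | 63% | 0.45 |
| 120 mg | 41.6 ± 37.6 | 90% | 0.35 |
| 144 mg | 30 ± 7 | 23% | 0.21 |

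Trough per mg varies 2.2-fold across sources, and the highest dose has the lowest mean. For 120 mg/day the section says "peak serum concentrations are >100 ng/ml", so peak over mean trough exceeds 100/54 = 1.9 or 100/41.6 = 2.4. At the goal dose no scaling is needed: 10 to 30 ng/ml straddles 20.

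**3. The calendars.**
- Sample window: 28 ± 7 = Day +21 to +35. Weaning starts: 28 ± 2 = Day +26 to +30.
- A patient on 20 mg twice daily who stops on Day +26 and is drawn on Day +35 is 35 − 26 = 9 days off drug.
- A patient on 40 mg twice daily who starts the one-week step-down on Day +26 is on the reduced dose to Day +33. At Day +35 that patient is 2 days off drug.
- The adherence period ends at Day +28. Even if the days after a Day +26 stop were counted as missed, adherence would be 26/28 = 93%, which passes.
- Before transplant, the start is Day -9 to -5 and the draw Day -3 to -1, so exposure is 2 to 8 days. All of it is at 20 mg twice daily, because Section 2.4.1 places the increase on Day 0.

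**4. Share below 20 ng/ml, as illustration only.** Assume proportional scaling and a lognormal trough, with σ² = ln(1 + CV²), μ = ln(mean) − σ²/2 and share = Φ((ln 20 − μ)/σ). At 80 mg/day the three means become 36, 27.7 and 16.7 ng/ml, and the shares are 23%, 49% and 82%. At 40 mg/day they are 68%, 81% and nearly 100%. Section 2.5 claims linear kinetics only above 30 ng/ml, and most of these scaled means lie below that.

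**5. Dilution, as illustration.** Take 15 v 15, a two-sided 5% t test, and a share f of treated samples that carries no drug effect, so that the mean effect is d(1 − f). A difference of 1.06 SD gives 80% power at f = 0. Power is 56% at f = 25% and 29% at f = 50%. The documents give no value for f.

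**6. Precision of a heart-rate contrast.** Half-width = t × SD × √(1 − r²) × √(2/n), with SD and r assumed.
- n = 15, SD 14, r = 0: 2.048 × 14 × 0.365 = 10.5 bpm.
- n = 20, SD 10, r = 0.5: 2.024 × 10 × 0.866 × 0.316 = 5.5 bpm.

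**The case against.** The case for the plan has several sound parts.

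- Section 2.5 calls prediction difficult, not impossible, and goes on to use human data to support the dose.
- Adherence includes nursing records as well as pill counts.
- The primary objective concerns administration, and Section 5.2 says that the study is mainly to give effect sizes with confidence intervals. A null result answers that objective.
- Heart rate is collected, so a crude group check of blockade could be made later.

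All of this stands, and it limits the point to attribution. It does not rescue the claim that the filter secures exposure, and it does not touch the overlap of the sample and weaning windows.

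A reader might infer more than the documents support:

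- *That patients below 20 ng/ml were not blocked.* The figure is a mouse level tied to tumour progression, and Section 1.3 gives it with a range (0.16 to 0.26 ng/ml) that does not contain it. Sections 1.3 and 2.4.1 allow that 20 mg twice daily, or a wide range of concentrations, may be effective. The shares in step 4 are trough shares, not shares with failed blockade.
- *That untimed draws are known to distort CTRA.* Section 5.3.1 describes a basal shift over extended periods of stress. Nothing shows that it follows serum swings within a dosing interval, so a fixed clock window for draws is not justified.
- *That a null CTRA result without heart-rate separation should be declared inconclusive by rule.* With a half-width of 5.5 to 10.5 bpm, lack of separation could be imprecision alone. A contrast by randomised arm also describes a different population from the adherence-filtered CTRA set.

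**Conclusion.** The concern holds as a limit on interpretation. The 80% filter measures intake, and the planned gene analysis contains no measure of exposure or blockade at the draw. A null CTRA result would inform the effect of giving propranolol but could not be attributed to blockade leaving expression unchanged.

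The firmest part rests on the calendars alone: samples on a reduced dose, or up to 9 days after the last dose, can enter the analysis as exposed. How many will do so is unknown. The exposure argument rests on the stated 10 to 30 ng/ml around a 20 ng/ml target, without scaling. The percentages in step 4 and the power figures in step 5 depend on assumptions that the documents do not supply and should not be quoted as findings. The point does not undermine the randomised design or the feasibility aim. It should be settled before the samples are analysed.

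**What to change.** 1. **Section 4.4.** Record draw date and time for every sample and, for propranolol patients, current dose and the date and time of last dose. Reconcile the sample window in Table 4.7a with the weaning window in Section 2.4.3. How to do so is for the investigators; nothing here asks for a change in dosing.
2. **Section 5.3.1.** Remove the statement that the filter secures sufficient exposure and describe it as a restriction on intake. Flag Day +28 samples drawn after weaning began, and pre-specify the CTRA estimate with and without them as a sensitivity analysis.
3. **Section 5.3.1, supportive only.** Report the baseline-adjusted heart-rate difference with its 95% CI, using the recorded value nearest the draw. Give it both by randomised arm and in the same patients as the CTRA analysis. Attach no decision rule.

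The cost is a few form fields and a small analysis of data already collected. Post-transplant heart rate is noisy (step 6). Table 4.7b shows no heart-rate entry at Day -2, and a sample drawn well away from Day +28 may lack a close reading. The contrast can support an interpretation but cannot settle it.
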